2.1 Sample Size and Power

Forty-five (45) patients <18 years of age were randomized at an experimental-to-control allocation of 2 to 1 in order to obtain approximately 36 completers, assuming an approximate drop-out rate of 20%. At a 1-sided significance level of $\alpha_{1\text{-sided}} = 0.025$, assuming a pooled standard deviation (SD) of 1.0, and a difference between the treatment groups of 1.2 in mean change in pruritus score from baseline to Month 6 favoring the experimental arm, the power of the study is 0.909, using the exact method (Proc Power, SAS v.9.4, Cary, NC). The key secondary endpoint is also powered for a standardized treatment effect (treatment effect/SD) of 1.2.

2.2 Blinded Sample Size Re-Estimation

Blinded sample size re-estimation (SSR) is classified as a well-understood adaptive feature in the FDA guidance [4] because it does not involve treatment unblinding and can be conducted without worrying about introducing bias into a trial. This one-sample variance SSR method [5] is based on non-comparative blinded data for which no alpha adjustment is required. If the pooled SD was overestimated in the original sample size calculation, the sample size will not be decreased. If the pooled SD was underestimated in the original sample size calculation, the sample size will increase up to 54 to maintain the study power ≥ 0.80 to detect a standard effect size of ≥ 0.83 at a significance level of $\alpha_{1\text{-sided}} = 0.025$, assuming the same 1.2 treatment difference in mean change in pruritus score from baseline to Month 6 (Week 21 to 24) as the original sample size calculation.

After a minimum of 18 patients in the experimental cohort have completed the Week 16 visit, the pooled SD of change from baseline to Month 4 (Weeks 13 to 16 assessments) and available change from baseline to Month 6 (Week 21 to 24) in average monthly scratching score will be calculated by an independent blinded statistician from Contract Research Organization (CRO), Firma Clinical. The independent blinded statistician will provide the following statement to the Sponsor: "The observed pooled SD at Week 16 and Week 24 available data is x.xxx. This estimate is based on xx subjects with non-missing outcome at Week 13 to 16 and xx subjects with non-missing outcomes at Week 21 to 24." The process of the blinded SSR will be documented by Firma Clinical in the Blinding and Unblinding Plan for Protocol A4250-012 prior to performing the blinded SSR.

CCI patients are expected to complete Visit Week 24 at the time of the blinded SSR. Based on scratching data from Study A4250-005 in the progressive familial intrahepatic cholestasis (PFIC) indication, the Month 6 pooled SD from the CCI patients is approximately CCI of the pooled SD based on Month 4 data from the CCI patients and Month 6 (Week 21 to 24) data from the CCI patients. Therefore, a multiplication factor CCI is applied when calculating the standard effect size at Week 24 in Table 4. The Sponsor will determine the number of completers per the sample size calculation listed in Table 4. The number of additional patients to be enrolled will be based on the actual dropout rate.

Table 4 – Blinded sample size re-estimation

Observed Pooled SD at Week 16 & Week 24 available data	Standard effect size at Week 24	N	Power
≤0.95	≥1.18	36	≥0.90
>0.95 to ≤0.98	≥1.14 to <1.18	39	≥0.90
>0.98 to ≤1.03	≥1.09 to <1.14	42	≥0.90
>1.03 to ≤1.10	≥1.02 to <1.09	45	≥0.88 to <0.90
>1.10 to ≤1.17	≥0.96 to <1.02	48	≥0.86 to <0.88
>1.17 to ≤1.25	≥0.90 to <0.96	51	≥0.84 to <0.86
>1.25 to ≤1.35	≥0.83 to <0.90	54	≥0.80 to <0.84
>1.35	<0.83	54	<0.80

Assuming a significance level of alpha 1-sided = 0.025 and 1.2 treatment difference in mean change in scratching score from baseline to Month 6
 N: Number of completers.

3 Analysis Populations

The following populations for analyses are defined:

Table 5 - Populations for analyses

Population	Description
Randomized	All patients from the screened population who have been allocated to a randomized intervention by IWRS regardless of whether the intervention was received or not.
Full Analysis Set (FAS)	All randomized patients who received at least 1 dose of study drug treatment. Patients will be analyzed in the treatment group they were randomized to even if they received the incorrect study drug. The FAS will be utilized for efficacy analyses.
Per Protocol Analysis Set (PPS)	The PPS is a subset of the FAS and will consist of all randomized patients for whom no important protocol deviation (i.e., no major protocol deviation which may affect the study efficacy outcomes) is documented. In addition, patients meet following criteria will be excluded from PPS. 
• Overall treatment compliance is less than 70%• Treatment duration is less than 50% of the days with eDiary data collected during weeks 21 to 24 The PPS will provide supportive data for the efficacy analyses. The algorithm for PPS will be defined and allocation of patients to the PPS will be performed before the database lock and un-blinding of the study.
Safety Analysis Set (SAF)	All patients who received at least 1 dose of study drug. Patients will be analyzed according to the treatment they actually received for the first dose. The SAF will be utilized for safety analyses.

A listing for each analysis set will be provided. The reason for exclusion from PPS will be summarized by treatment groups and will be included in a listing.

4 Statistical Analyses

4.1 General Considerations

All personnel involved with the analysis of the study and the independent blinded statistician who performs the blinded SSR will remain blinded until database lock except the unblinded Data Safety Monitoring Board (DSMB) statistician/programmers from Firma who are independent from both the Firma study team and Albireo. All statistical procedures will be completed using SAS[®] version 9.4.

In general, continuous data will be summarized using descriptive statistics, including the number of observations available (n), mean, SD, median, minimum, and maximum. The letter “n” will be presented without a decimal point. Minimum and maximum values will be presented to the same precision as in the database. Mean and median will be presented to 1 more decimal place than the minimum and maximum. SD will be presented to 1 more decimal place than the mean and median.

Categorical and ordinal data will be summarized using the count (frequencies) and percentage of patients. Percentages will be rounded to 1 decimal place. Descriptive summaries of change from baseline in categorical variables will be provided using shift tables, as applicable.

For summary purposes, if not otherwise specified, the baseline value of a parameter is defined as the last available assessment of that parameter prior to the first intake of study drug. Derived variables used for the analyses are provided in [Appendix 2](#). All summaries will be presented by treatment group, unless otherwise specified.

For summary tables, if not otherwise specified, the following 2 presentations will be used:

- For baseline related tables and protocol deviations: by treatment group (odevixibat and placebo) and overall (2 treatment groups combined) will be presented.
- For the safety and efficacy related tables: by treatment group (odevixibat and placebo) will be presented.

The analysis window details for the derivation of study weeks are outlined in [Appendix 3](#).

Age is the stratification factor for the study. Since the purpose of stratification in the randomization is to balance the treatments in each stratum and following the intend-to-treat principle, for any analysis based on the FAS where strata is used for covariate adjustment of the modeling (with the exception of subgroup analyses), the strata of age that is recorded in the randomization system (IWRS) will be used. For all other analyses based on the FAS and all subgroup analyses, the actual age will be used to categorize the age groups.

Selected patient data, including derived data, will be presented in individual patient data listings. All listings will be sorted by treatment group, patient number, date/time and visit. Each patient’s sex and age at randomization will be stated on each listing. Data listings will be based on all randomized patients.

4.2 Patient Dispositions

The number (%) of patients in the following categories will be provided:

- Patients randomized
- Patients dosed
- Patients not dosed
- Patients completing treatment
- Patients discontinuing treatment early (including reason for discontinuation of treatment)
- Patients completing Study A4250-012
 - Patients discontinuing treatment
 - Patients enrolled into Study A4250-015
 - Patient did not enroll into Study A4250-015
- Patients withdrawing early from the study (including withdrawal reason)

Additionally, patients enrolled, included in the SAF, in the FAS, and in the PP analysis set will be summarized by region ([Appendix 4](#)).

Summary table for patients with premature discontinuation of study drug treatment, undergoing biliary diversion surgery and liver transplantation will be provided.

Protocol deviations

Important protocol deviations (IPD) will be identified by study team according to the criteria defined prior to database lock. IPDs will include following categories:

- Failure to meet following inclusion or exclusion criteria
 - Inclusion criteria (2) Patient must have a history of significant pruritus and a caregiver reported observed scratching or a patient -reported pruritus score at an average of ≥ 2
 - Inclusion criteria (3) Patient must have an elevated baseline serum bile acid level.
- Non-compliance in study procedure
 - Missing pruritus score at month 6 due to insufficient eDiary data collected during weeks 21-24

The number of patients with protocol deviations due to COVID-19 and number of protocol deviation due to COVID-19 will be summarized in the FAS.

In addition, a listing will be provided with all protocol deviations identified based on data recorded on protocol deviation logs (on randomized patients) prior to database lock.

4.3 Demographics and Baseline Characteristics, Prior or Concomitant Medications

Demographics, baseline and disease characteristics

The following demographics, baseline and disease characteristics, medical and surgical history will be summarized using descriptive statistics in the FAS.

Demographic, baseline, and disease characteristics

- Age in years as quantitative variable and Age in years as categorical variables (Age group 1: 0 to <10, 10 to <18; Age group 2: 0 to <2, 2 to <12, 12 to <18) based on actual age.
- Age group (0 to <10, 10 to <18) from IWRS for randomization
- Gender (Male, Female)
- Race (American Indian or Alaska Native, Asian, Black or African American, Native Hawaiian or Other Pacific, Islander, White, Other, Not reported)
- Race group (White, Non-White (including race as not reported))
- Ethnicity (Hispanic or Latino, Not Hispanic or Latino, Not reported)
- Ethnicity group (Hispanic or Latino (including ethnicity as not reported), Not Hispanic or Latino)
- Country and region ([Appendix 4](#))
- Use of ursodeoxycholic acid (UDCA)
- Use of anti-pruritus medication
- Baseline values: height (or length depending on age), weight as quantitative and categorical (≤ 10 and > 10 kg) variable, body mass index (BMI), Z-score (height, weight, and BMI), pruritus score (i.e., AM, PM, average AM and PM scratching score from ObsRO), serum bile acid as quantitative and categorical (\geq median and $<$ median based on overall randomization population) variable, estimated glomerular filtration rate (eGFR), ALT, AST, gamma-glutamyl transferase (GGT), total bilirubin, direct bilirubin as quantitative and categorical (> 3 and ≤ 3 mg/dL), alkaline phosphatase (ALP), INR, cholesterol, triglycerides, vitamin A, vitamin E, and 25-hydroxy vitamin D.
- Disease characteristics include
 - Genetic testing results for ALGS if performed at screening (e.g., mutation in *JAG1* vs *NOTCH2*; per protocol, testing is only performed at screening if not available in the patient's medical record), years since ALGS diagnosis
 - Child-Pugh classification (mild (Class A), moderate (Class B), or severe hepatic impairment (Class C)), and hepatic impairment classification (no impairment, mild, moderate, or severe) per NCI Organ Dysfunction Working Group [6]. Details of the classification are described in [Appendix 9](#).

eGFR will be calculated based on the modified/bedside Schwartz equation. The values of eGFR will be provided by the central laboratory vendor.

Listings will be created to present all the demographic, baseline, and disease characteristics for all randomized patients.

Medical surgical history

Medical and surgical history includes date of diagnosis of ALGS, prior medications for ALGS, historical (2 years prior to Screening) liver function test (LFT) values (AST, ALT, and total bilirubin), previous genetic testing for ALGS, and historical biopsy data.

Medical and surgical history will be coded to a preferred term (PT) and associated primary System organ class (SOC) using the Medical Dictionary for Regulatory Activities (MedDRA) version 25.0. The frequencies and percentages of patients with reported medical and surgical history will be presented by SOC and PT for the SAF. The summary table will be sorted alphabetically for SOC and PT. Medical and surgical history will also be listed.

Prior or concomitant medications

All medications will be coded using the World Health Organization-Drug Dictionary (WHO-DD) using the version March 2022.

- Prior medications are any medications taken by the patient within 3 months prior to first intake of study drug that is recorded on the eCRF. Prior medications can be discontinued before the first intake of study drug or can be ongoing during the treatment period.
- Concomitant medications are any medications received by the patient concomitantly on or after the first intake of study drug.

Prior and concomitant medications will be summarized descriptively using frequency tables by Anatomical Therapeutic Chemical (ATC) and PT for the SAF. ATC class 4 and PT will be presented alphabetically. All prior and concomitant medications will be listed. Details for imputing missing or partial start and/or stop dates of non-study medications are described in [Appendix 5](#).

4.4 Extent of Exposure

The extent of exposure will be assessed by the duration of treatment exposure, average daily dose, and compliance. Exposure will be summarized with descriptive statistics (n, mean, median, SD, minimum, and maximum) and presented using the SAF. In addition, duration of treatment exposure will be summarized categorically: ≤ 4 weeks, $>4 - \leq 8$ weeks, $>8 - \leq 12$ weeks, $>12 - \leq 16$ weeks, $>16 - \leq 20$ weeks, $>20 - \leq 24$ weeks, and >24 weeks.

Duration of exposure (in weeks) = (Date of last study drug intake – Date of first study drug intake + 1)/7. Investigators are allowed to interrupt the study drug to allow adverse events to resolve, if necessary. Any drug interruption will not be considered when calculating the treatment duration.

Average daily dose (ug/kg/day) = Sum of (number of capsules taken per day * dose strength of the capsules per weight category * dose duration under this dose amount/weight) / (Date of last study drug intake – Date of first study drug intake + 1). Intake dose and the corresponding dose duration is collected on the dosing administration page of the eCRF.

Treatment Compliance = $100 \times \text{sum of (number of capsules actually taken) / sum of (number of capsules planned to be taken per day * dose duration under this planned dose amount)}$. The denominator is calculated as the prescribed number of capsules (based on body weight at each visit; refer to Protocol Table 2 and 3 for the details) multiplied by the treatment period (regardless drug interrupted).

Subgroup analysis based on the Age group 1 (i.e., 0 to <10 years vs. 10 to <18 years which categorized based on the actual age) will be provided for the exposure and compliance rate. In addition, treatment compliance will be summarized quantitatively and categorically: <80%, between 80% and 120%, and >120%.

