### 8.2 Administration of Study Drug

Patients will be dosed with odevixibat at a dose of 120 µg/kg/day or placebo for 24 weeks. Dose modification is permitted per [Section 8.3](#). Study drug will be dispensed to the patient from randomization (Study Day 1) through the Week 20 visit, together with instructions on how to store and take the drug.

Odevixibat is to be taken in the morning, together with food. On clinic visit days when laboratory assessments are conducted, the study drug is to be taken after the visit and after laboratory samples are taken. The capsule(s) is/are not to be crushed or chewed. When swallowing the capsule intact, the dose is to be administered with a glass of water.

For a patient unable to swallow a capsule intact, the capsule can be opened, and the contents sprinkled and mixed in a small amount of soft room temperature yogurt, apple sauce, or fruit purée. A list of food options can be found in the Pharmacy manual. The amount of food is to be less than what the patient/infant would be expected to eat and is to be followed by water. For infants who are not yet weaned onto solid foods, the pellets can be administered as a suspension in infant formula or breast milk using an appropriate dosing device (e.g. an oral dosing syringe).

1. Hold the capsule over the prepared food, gently twist open and allow the content to fall into food
2. Mix the entire capsule content with 1 or 2 tablespoons (15 mL to 30 mL) of soft food (apple sauce, fruit purée, or yogurt)
3. Administer the mixture immediately after mixing

The number of capsules provided to the patient will be based on body weight at randomization (Study Day 1) and can be adjusted depending on the patient's weight (identified in [Table 2](#)) at each study visit.

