4.5.2.1 Main Analysis

The primary efficacy analysis for the primary endpoint will be performed on the FAS and will be based on a MMRM excluding data after ICEs of biliary diversion surgery or liver transplant and data collected after treatment discontinuation will be included.

The change from baseline for each 4-weeks (monthly) average AM and PM scratching score will be analyzed with the SAS PROC MIXED using a restricted maximum likelihood (REML) with baseline age stratification, baseline average AM and PM scratching score, baseline direct bilirubin, treatment group, time (in months, this is a categorical variable, i.e., 1-4 weeks, 5-8 weeks, 9-12 weeks, 13-16 weeks, 17-20 weeks, and 21-24 weeks), and treatment-by-time interaction in the model. Baseline direct bilirubin is expected to be associated with the treatment effect. Unstructured covariance matrix (UN) will be used in the analysis. If this analysis fails to converge, the following structures will be tested in this order: Toeplitz (equal variances and a separate correlation for each level of separation between the time points), AR(1) (first-order autoregressive, equal variances and exponentially decreasing correlations), compound symmetry (CS) (equal variances and equal pairwise correlations across fixed time points). The first (co)variance structure yielding convergence will be used as the primary analysis. The Kenward-Roger approximation will be used to estimate denominator degrees of freedom. The primary comparison will be the difference of the least square mean (lsmean) estimate between odevixibat and placebo at Month 6 (Weeks 21 to 24). The difference of the lsmean estimate between odevixibat and placebo at other Months will be estimated and tested. Average treatment effect between odevixibat and placebo at Month 4 to 6 will be also estimated and tested.

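### Compliance is a ratio of capsule totals, so when the daily capsule count changes, equal adherence can fall on either side of the 70% per-protocol cut-off

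*SAP*

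**What the plan says.** SAP 4.4 (Extent of Exposure), repeated in SAP Appendix 2, Table 9, divides the sum of capsules taken by the sum of "number of capsules planned to be taken per day * dose duration under this planned dose amount". SAP 4.4 then explains the denominator: "The denominator is calculated as the prescribed number of capsules (based on body weight at each visit; refer to Protocol Table 2 and 3", and this is "multiplied by the treatment period (regardless drug interrupted". Days of interruption therefore count as missed. The SAP version history confirms that this was a deliberate change in version 2.0.

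Protocol 8.2 says: "The number of capsules provided to the patient will be based on body weight at randomization (Study Day 1) and can be adjusted" according to weight at each visit. SAP 1.1 repeats this permissive rule.

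The compliance figure has two uses:

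- SAP Section 3, Table 5 removes a patient from the per-protocol set (PPS) if "Overall treatment compliance is less than 70" per cent.
- SAP 4.4 tabulates compliance as below 80%, 80 to 120%, and above 120%.

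On the role of the set, Table 5 states: "The PPS will provide supportive data for the efficacy analyses".

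**The concern.** A ratio of capsule totals measures adherence fairly only if the planned daily count stays constant, or if missed days are spread in proportion over the periods with different counts. Neither is assured here. All nine weight boundaries in Protocol Table 2 change the count. Below 8 kg, a reduction from Table 2 to Table 3 changes it too (for example 4 capsules to 1 at 7 kg). Missed days may also come in blocks, because the protocol interrupts study drug for liver criteria (10.2.2.1), diarrhea (10.2.2.4) and persistent vitamin deficiency (10.2.2.5), and the formula counts those days as missed.

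Two children with the same share of days taken can then be classified differently for the PPS, depending only on whether the gap came before or after the count changed. Diarrhea is an expected effect of the drug (Protocol 5.5), so such gaps could be unequal between arms, although the documents do not show that they are. With 45 children randomized 2:1, the placebo arm has about 45/3 = 15, so one misallocated child is a visible share of the PPS.

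A second, smaller issue is the wording. If a child crosses a band and the prescription is left unchanged, the SAP does not say whether the planned count is the one prescribed or the one that the table gives for the new weight.

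**Working it through.** The plan states no compliance figure to reproduce, so the check applies its formula to its own dosing tables.

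**Inputs.** Treatment lasts 24 weeks = 168 days (Protocol 8.2). Daily counts come from Protocol Tables 2 and 3. The cut-off is 70% (SAP Table 5). Crossing times and missed-day patterns are assumptions, because the documents give no growth or adherence data. Days that are not missed are assumed to be taken in full.

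**Formula.** Let the daily count be n1 for d1 days and then n2 for d2 days. Planned capsules P = n1·d1 + n2·d2. If m days are missed, compliance is 100·(P − m·n1)/P when all fall before the change, and 100·(P − m·n2)/P when all fall after it. The share of days taken is 100·(168 − m)/168.

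**1. Prescription adjusted correctly, change at Week 12 (d1 = d2 = 84)**

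| Change | P | Missed days | All before | All after | Days taken |
|---|---|---|---|---|---|
| 19.5 kg, 4 to 2 | 504 | 40 | 344/504 = 68% | 424/504 = 84% | 128/168 = 76% |
| 19.5 kg, 4 to 2 | 504 | 60 | 264/504 = 52% | 384/504 = 76% | 108/168 = 64% |
| 12.5 kg, 2 to 3 | 420 | 50 | 320/420 = 76.2% | 270/420 = 64.3% | 118/168 = 70.2% |
| 7 kg, Table 2 to Table 3, 4 to 1 | 420 | 42 | 252/420 = 60% | 378/420 = 90% | 126/168 = 75% |

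At 19.5 kg the daily dose is 2400 µg on both sides, so the two patterns miss the same amount of drug. For this crossing, any number of missed days from 38 (352/504 = 69.8% against 428/504 = 84.9%) to 75 (204/504 = 40.5% against 354/504 = 70.2%) puts the two patterns on opposite sides of 70%.

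**2. Missed days spread evenly.** If a fraction f is missed in each period, compliance is (P − f·P)/P = 1 − f, the share of days taken. There is no distortion.

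**3. Prescription not adjusted, everything dispensed is taken, denominator read from the table at the visit weight, upward crossing at Week 4 (Day 28)**

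- 12.5 or 25.5 kg (2 to 3): 336/(56 + 420) = 336/476 = 70.6%.
- 6, 17.5 or 35.5 kg (3 to 4): 504/(84 + 560) = 504/644 = 78.3%.
- 8 or 19.5 kg (4 to 2): 672/(112 + 280) = 672/392 = 171.4%.

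At 80% adherence with 12.5 kg crossed at Week 8, the result is 0.8 × 336/(112 + 336) = 268.8/448 = 60%.

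**4. Would weighting by µg work?** At 19.5 kg it would. Elsewhere it would not. For 8 kg crossed at Week 12, planned drug is 84 × 800 + 84 × 1200 = 168,000 µg. Then 42 missed days give (168,000 − 33,600)/168,000 = 80% if before and (168,000 − 50,400)/168,000 = 70% if after, against 75% of days taken. At the seven boundaries where capsule strength does not change, µg is proportional to the count and nothing improves.

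**5. Per-day ratio.** Take 100·Σ(taken in interval ÷ daily count prescribed)/Σ days. For 19.5 kg with 40 missed days before the crossing: (176/4 + 168/2)/168 = (44 + 84)/168 = 76%. With the missed days after it: (336/4 + 88/2)/168 = (84 + 44)/168 = 76%. In step 3, every fully adherent child scores 100%.

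**The case against.** Four arguments weigh against the point.

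- **The denominator may already be the assigned number.** A reader might infer that the SAP resets planned capsules from weight at every visit and so contradicts the protocol. The text does not establish this. It speaks of the prescribed number and of duration under the planned dose amount, and the words on body weight can be read as explaining how the prescription is set. The reference to Table 3 supports that reading, because a reduction is the investigator's decision (Protocol 8.3) and cannot be derived from weight. This argument stands: the wording is an ambiguity, not a proven conflict, and nothing shows that unadjusted crossings occur.
- **Full adherence does not lead to exclusion when weight rises.** A reader might infer from step 3 that a fully adherent growing child drops out of the PPS. None does, since the lowest value is 70.6%. Exclusion by that route needs real non-adherence as well, or a downward crossing.
- **Mixed capsule strengths are not the cause.** A reader might blame the adding of capsules of different strength. The effect also appears at 12.5 kg, where strength is 600 µg on both sides. The changing count drives it. From 8 kg up, a reduction to Table 3 leaves the count unchanged.
- **The scenarios are special and the stakes are small.** A change in count and clustered missed days are both needed, and the number of children affected may be zero. SAP 4.4 also reports average daily dose in µg/kg/day, and the PPS allocation is settled before unblinding, so a value such as 171% could be queried. This argument holds for the size of the point. It does not remove the defect: 68% looks like an ordinary value, and block interruptions are a realistic source of clustering.

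**Conclusion.** The point holds in a limited form. The capsule-count ratio gives a missed day more weight when the planned count is higher, even if every prescription follows the tables. In the 19.5 kg example the gap is 16 percentage points (68% against 84%) around a share of days taken of 76%, and it straddles the PPS cut-off. The result rests on an assumed crossing at Week 12 and on missed days lying wholly on one side of it. How often this happens cannot be estimated from the documents. The unclear wording of the denominator is a separate matter that needs one clarifying sentence.

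Nothing here supports the inference that the main result is at risk. SAP 4.5.2.1 states: "The primary efficacy analysis for the primary endpoint will be performed on the FAS". That analysis, alpha and power do not depend on compliance. The reach is the supplementary PPS analyses of the primary and key secondary endpoints, and the descriptive compliance tables.

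**What to change.** In SAP 4.4 and Table 9:

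1. State that the planned count is the number of capsules per day actually prescribed for each interval, and that it is not re-derived from weight if the prescription was left unchanged. Start a new interval whenever the prescribed count changes.
2. Define compliance as 100 × Σ(capsules taken in the interval ÷ capsules prescribed per day in that interval) ÷ Σ(days in the interval), with interruption days kept in the denominator.
3. Use this measure both for the 70% PPS criterion and for the 80% and 120% categories.

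A µg-weighted ratio should not be offered as an alternative, because it corrects fully only at 19.5 kg.

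The cost is a few sentences and a small change to the compliance program. Intake and its duration are already collected on the dosing page (SAP 4.4), returned drug is counted at each visit (Protocol 8.6), and dose modifications are recorded (Protocol 8.3). The change has to be made before the PPS is allocated and the database locked. No dose or dosing rule is touched.
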